10.1 Regulatory and ethical compliance

This clinical study was designed and shall be implemented, executed and reported in accordance with the ICH Harmonized Tripartite Guidelines for Good Clinical Practice, with applicable local regulations (including European Directive 2001/20/EC, US CFR 21, and Japanese Ministry of Health, Labor, and Welfare), and with the ethical principles laid down in the Declaration of Helsinki.

10.2 Informed consent procedures

Eligible patients/subjects may only be included in the study after providing written (witnessed, where required by law or regulation), IRB/IEC-approved informed consent, or, if incapable of doing so, after such consent has been provided by a legally acceptable representative(s) of the patient. In cases where the patient's representative gives consent, the patient must be informed

about the study to the extent possible given his/her understanding. If the patient is capable of doing so, he/she must indicate assent by personally signing and dating the written informed consent document or a separate assent form. Informed consent must be obtained before conducting any study-specific procedures (e.g. all of the procedures described in the protocol). The process of obtaining informed consent must be documented in the patient source documents.

Novartis will provide to investigators in a separate document a proposed informed consent form that complies with the ICH GCP guideline and regulatory requirements and is considered appropriate for this study. Any changes to the proposed consent form suggested by the investigator must be agreed to by Novartis before submission to the IRB/IEC, and a copy of the approved version must be provided to the Novartis monitor after IRB/IEC approval.

10.3 Responsibilities of the investigator and IRB/IEC

Before initiating a trial, the investigator/institution must obtain approval/favorable opinion from the Institutional Review Board/Independent Ethics Committee (IRB/IEC) for the trial protocol, written informed consent form, consent form updates, subject recruitment procedures (e.g., advertisements) and any other written information to be provided to patients/subjects as per local law and regulations. Prior to study start, the investigator is required to sign a protocol signature page confirming his/her agreement to conduct the study in accordance with these documents and all of the instructions and procedures found in this protocol and to give access to all relevant data and records to Novartis monitors, auditors, Novartis Quality Assurance representatives, designated agents of Novartis, IRBs/IECs, and regulatory authorities as required. If an inspection of the clinical site is requested by a regulatory authority, the investigator must inform Novartis immediately that this request has been made.

10.4 Publication of study protocol and results

The key design elements of this protocol will be posted in a publicly accessible database such as clinicaltrials.gov. In addition, upon study completion and finalization of the study report the results of this trial will be submitted for publication and/or posted in a publicly accessible database of clinical trial results (as applicable).

11 Protocol adherence

This protocol defines the study objectives, the study procedures and the data to be collected on study participants. Additional assessments required to ensure safety of patients/subjects should be administered as deemed necessary on a case by case basis. Under no circumstances is an investigator allowed to collect additional data or conduct any additional procedures for any research related purpose involving any investigational drugs under the protocol.

Investigators ascertain they will apply due diligence to avoid protocol deviations. If an investigator feels a protocol deviation would improve the conduct of the study this must be considered a protocol amendment, and unless such an amendment is agreed upon by Novartis and approved by the IRB/IEC and health authorities, where required, it cannot be implemented.

eGFR	Estimated glomerular filtration rate
EQ-5D	EuroQol five dimensions questionnaire
ESC	European society of cardiology
GFR	Glomerular filtration rate
HF	Heart failure
KCCQ	Kansas City cardiomyopathy questionnaire
LVEF	Left ventricular ejection fraction
MDRD	Modification of diet in renal disease
MedDRA	Medical dictionary for regulatory activities
MRA	Mineralocorticoid receptor blocker
MRI	Magnetic resonance imaging
NP	Natriuretic peptide
NT-proBNP	N-terminal prohormone of brain natriuretic peptide
NYHA	New York heart association
PT	Preferred term
QC	Quality control
QoL	Quality of life
SAP	Statistical analysis plan
SDVP	Structure and data validation plan

SOC	System organ class
VAS	Visual analogue scale
WHO	World health organization

Definition of terms

A1: Assessment of the patient's treatment at Visit 1

A2: Assessment of the patient's treatment at Visit 2

A3: Assessment of the patient's treatment at Visit 3

1 Study protocol and scope

This Statistical Analysis Plan (SAP) describes the planned analyses for the final analysis of the low-interventional PREFER study. It is based on the final version 00 of the protocol, dated 15 February 2016.

2 General definitions and procedures

2.1 Software

Statistical analyses will be carried out with the SAS® package (version 9.4 or higher).

2.2 Coding

Concomitant diseases and adverse events (AEs) are coded by means of the Medical Dictionary for Regulatory Activities (MedDRA dictionary), English version (latest version available at the start of coding).

Therapy of heart failure (HF) and concomitant medication will be coded by means of the WHO Drug Dictionary including anatomical therapeutic chemical (ATC) classification up to level 4 and preferred name (latest version at the start of coding).

2.3 Procedures prior to statistical analysis

Prior to the final analysis data cleaning procedures as described in section 2.5 will be performed. Subsequently, an export of the electronic case report form (eCRF) data will be performed providing the source data base for the final analysis.

Thereafter, only the responsible data manager and the project statistician will be privileged to have access to this data base. Any changes to the analyses after the SAP has been finalized will be clearly described in the study report.

After data base closure, the data will be transferred electronically to the statistical software package SAS® data set format for statistical analysis. The SAS® data sets will be considered as source data sets for statistical analysis.

2.4 Reporting standard

An integrated clinical study report in English language according to [redacted] standards will be generated.

2.5 Quality control

Data validation is carried out according to the Structure and Data Validation Plan (SDVP, version 6.0, 20 March 2018). The SDVP defines criteria and responsibilities for general and medical plausibility checks of the data. Prior to the final analysis, a comprehensive cleaning of the available data with respect to the criteria defined in the SDVP is performed. This comprehensive cleaning includes an enforced data and query review aiming to solve any inconsistencies within the data. The quality control includes

checking for completeness, correctness and plausibility, and is carried out by the data management department in cooperation with the responsible medical advisor.

The SAP is consistent with the underlying protocol. If there is a need for deviating substantially from the protocol-defined analysis, this is described in detail. The methods described in this SAP are mandatory for statistical programming.

Quality control (QC) of statistical programming will be performed according to the QC plan, which specifies all planned actions to ensure that the performed analyses are correct, traceable and in line with the planned analysis as specified in the SAP. The QC plan also includes filing of statistical programs, outputs and documentation of QC. It is finalized by the project statistical programmer before the start of any programming activities.

Documentation of QC is filed in the trial master file.

3 Study objectives

3.1 Primary objective(s)

The primary objective of this study is to assess if NT-proBNP measurement-guided cardiologist-referral of chronic heart failure (CHF) patients, who are currently judged by their primary care physician as being clinically stable^{*}, leads to optimization of HF treatment, defined as adherence[#] to level I-A treatment recommendations of the current[§] ESC guidelines for the treatment of HF.

***Note:** Within this study, clinically stable patients are defined as those patients, who by the judgement of their primary care physician currently do not require and, in the last 3 months prior to the Baseline visit have not had, any change in their pharmacological or device treatment of HF.

#Note: Adherence to the recommendations of the ESC guidelines within this study is defined as the prescription of all HF specific drugs with level I-A recommendation for a given patient's clinical status at a dose > 50% of the recommended daily dose.

§Note: Current ESC guidelines are those which are in force on the date the patient signs the informed consent form.

3.2 Secondary objective(s)

- To describe the Baseline demographic and clinical characteristics as well as pharmacological and device treatment of CHF patients managed in the primary care setting (in the total population of enrolled patients and also sub-grouped into different European country and patient characteristics clusters).
- To assess in clinically stable patients the impact of patients' key Baseline characteristics on the cardiologists' and primary care physicians' prescription practice for HF treatment and the adherence of these treatment choices to the recommendations of the current ESC guidelines.
- To describe the blood levels of NT-proBNP in CHF patients managed in the primary care setting.

- To describe the proportion of CHF patients managed in the primary care setting considered as being clinically stable
- To describe local prescription practice of cardiologists for the treatment of clinically stable CHF patients with NT-proBNP levels ≥ 600 pg/ml.
- To describe local prescription practice and decision making of primary care physicians for the treatment of clinically stable CHF patients with NT-proBNP levels ≥ 600 pg/ml.
- To characterize how treatment optimization, defined as prescription of treatment regimens adherent to the recommendations of the ESC guidelines, affects NT-proBNP levels in clinically stable CHF patients with Baseline NT-proBNP levels ≥ 600 pg/ml.
- To assess the Baseline health-related quality of life (QoL) in CHF patients and describe the temporal course of QoL after specialist referral in clinically stable CHF patients with NT-proBNP ≥ 600 pg/ml by means of EQ-5D and KCCQ questionnaires.

4 Essential features of the study design

4.1 Type of study

This is an international, prospective, low-interventional study enrolling patients with CHF with reduced ejection fraction (LVEF $\leq 40\%$) who are managed in the primary care setting across Europe. The study comprises three visits over a period of maximum 10 months. Enrollment is planned to last 24 months.

4.2 Study population

According to the protocol, it was planned to enroll a total of 4000 CHF patients of which approximately 2400 are estimated to enter the prospective period (who are considered clinically stable and show NT-proBNP levels ≥ 600 pg/ml). The recruitment was to be regarded as completed once approximately 2400 patients have entered the prospective period irrespectively how many patients have been enrolled totally.

However, it was decided by Novartis to determine the study prematurely, i.e. to stop recruiting and data collection in March 2018: therefore, last patient first visit was on 07 March 2018, last patient last visit on 23 March 2018. This means, that not every subject was able to perform Visit 3 of the study.

Patients/subjects eligible for inclusion in this study had to fulfil all of the following criteria:

- Willing and able to provide written informed consent and accept study procedures and time schedule.

- Age \geq 18 years.
- Patients suffering from chronic heart failure (the heart failure diagnosis must have been made or confirmed by a cardiologist and/or hospital physician at any time in the patient's medical history).
- Patients with reduced ejection fraction ($\leq 40\%$) as confirmed at any time point in the patient's medical history.

Patients/subjects fulfilling any of the following criteria were not eligible for inclusion in this study.

- Use of investigational drugs either within 5 half-lives of enrollment, or within 30 days, or until the expected pharmacodynamic effect has returned to Baseline, whichever is longer.
- Major surgery in the last 3 months prior to Baseline or planned major surgery or cardiac intervention during the study.
- Cancer or other significant co-morbidities implying that the patient's condition is unstable.
- Comorbidities that can be associated with elevated natriuretic peptide (NP) levels: renal insufficiency (eGFR < 30 ml/min/1.73 m² calculated according to MDRD formula), recent (less than 3 months) cerebral trauma or recent (less than 3 months) cerebrovascular incident, novel diagnosis or acute exacerbation of COPD within the last 3 months.
- Patients who are primarily managed and regularly followed-up by a cardiologist for their HF
- Highly frail patients whose estimated lifespan due to comorbidities by the judgement of the investigator is less than 6 months.

4.3 Study treatment

The patients received the treatment that their primary care physician has decided to prescribe for their disease. Upon referral to the cardiologist the treatment modification was entirely in the discretion of the primary care physician.

4.4 Study schedule

The study comprised 3 visits: Baseline (Visit 1), Visit 2 (recommended max. 6 months after Baseline), Visit 3 (recommended at least 3 months and preferably not later than 4 months after Visit 2; max. 10 months after Baseline). At Baseline (Visit 1) all consecutive CHF patients who satisfied all inclusion and exclusion criteria were to be documented and should complete the QoL questionnaires. At this visit, the investigator assessed whether the patient's status was considered clinically stable (as defined in Section 3.1) and documented his/her decision. Thereafter, all patients underwent blood-sampling for on-site NT-proBNP measurement. Only patients considered clinically stable and with NT-proBNP levels ≥ 600 pg/ml were referred to a cardiologist for evaluation of treatment optimization. After the visit to the cardiologist, but no later than 6 months after the Baseline visit, the patient should return to the investigator's office for

Visit 2. At Visit 2, the patient should complete the QoL questionnaires and the cardiologist's recommendations was reviewed and documented by the investigator; at this visit, the investigator should document, if the cardiologist's recommendations or changes for the patient's HF treatment were followed or continued, respectively. The investigator should provide reasons if the recommendations were not followed and document the prescribed HF treatment. At Visit 3, not later than 10 months after Baseline, but no earlier than 3 months after Visit 2, the patient should return for the final visit, where clinical and QoL outcomes were documented. Thereafter, the patient underwent blood sampling for measurement of NT-proBNP levels.

[Table 4-1](#) lists all of the assessments and indicates with an "x" when the visits were performed.

Table 4-1 Assessment schedule

Visit number	Visit 1	Visit 2	Visit 3
Time of Visit and recommended visit windows	Baseline	After referral (max. 6 months after Baseline)	Min. 3 months, max 4 months after visit 2 (max. 10 months after Baseline)
Informed consent	X		
Inclusion/exclusion criteria	X		
Demographic and clinical history (incl. diagnostic and therapeutic procedures)	X	X ¹	X ¹
Height	X		
Body weight	X		X ¹
Physical examination incl. NYHA-Status and vital signs	X	X ¹	X ¹
Observation of ongoing drug/ non-drug treatment for HF	X	X ¹	X ¹
Observation of relevant laboratory tests, as available per routine care	X	X ¹	X ¹
EQ-5D questionnaire	X	X ¹	X ¹
KCCQ questionnaire	X	X ¹	X ¹
Assessment and documentation of clinical stability of patient	X		
NT-proBNP assessment	X		X ¹
Referral to cardiologist ¹	X ¹		
Recording of specialist advice/prescription on drug/ non-drug treatment modification ¹		X ¹	
Prescription and documentation of revised treatment in the discretion of primary care physician ¹		X ¹	
Observation of comorbidities and their changes during the study	X	X ¹	X ¹
Adverse events	X	X ¹	X ¹
Report adverse drug reactions to any medication and incidents with medical devices as per local regulations	X	X ¹	X ¹

¹ Applies only for patients who enter the prospective period, i.e. clinically stable patients with NT-proBNP ≥ 600 pg/ml

4.5 Measures

4.5.1 Primary measures

The primary effectiveness measure is the adherence (yes/no) of HF treatment to the current ESC guideline^{1, 2}. The following measures of HF therapy and concomitant medication will be used for derivation of the primary effectiveness measure:

- Active ingredient

- Single dose and dose unit
- Start and end date

Following the ESC guideline definitions, two levels of guideline adherence will be used for the analysis: adherence with respect to drug types (level 1) and adherence with respect to drug types **and** drug dose (level 2). The exact definitions of both levels of guideline adherence are provided in [Table 4-2](#).

Table 4-2 ESC guideline definitions

Guideline level	Criteria for guideline adherence
Drug types	Treatment with one [*] ACEi [°] or one [*] ARB ⁺ , in combination with one [*] beta-blocker ⁺ and one [*] MRA ⁺ for patients with an LVEF ≤ 35% at Visit 1 Treatment with one [*] ACEi [°] or one [*] ARB ⁺ , in combination with one [*] beta-blocker ⁺ without treatment with an MRA for patients with an LVEF > 35% at Visit 1
Drug type and dose	Guideline adherent with respect to drug types and dosage of all respective guideline drugs ≥ 50% of the recommended target dose [#]

^{*} exactly one

⁺ Only drugs with indication for treatment of HF will be considered as according to guidelines. Any use of a drug from the respective class with no indication for HF leads to treatment classified as non-adherent.

[°] Alternatively: Sacubitril/Valsartan

[#] In case a recommended target dose of a HF medication cannot be defined, the criterion for guideline adherence with respect to drug dose will be considered as fulfilled for this drug (independent from the actual dose)

For identification of the drugs relevant for guideline adherence the following implementations will be used:

- ACEi: ATC texts "ace inhibitors and diuretics", "ace inhibitors, plain"
- ARB: ATC texts "angiotensin ii antagonists and calcium channel blockers", "angiotensin ii antagonists and diuretics", "angiotensin ii antagonists, plain"
- Beta-blocker: ATC texts "alpha and beta blocking agents", "beta blocking agents, non-selective", "beta blocking agents, selective", "beta blocking agents, selective, and thiazides"
- MRA: ATC code C03DA

[Table 4-3](#) describes guideline relevant treatments with indication for HF and provides the respective target doses to be applied for the guideline analyses:

Table 4-3 Recommended target doses used for guideline analyses

Treatment	Recommended total daily target dose (mg)
ACEi	
Benazepril	40
Captopril	150
Cilazapril	10
Enalapril	20
Fosinopril	80
Lisinopril	35
Perindopril	16
Quinapril	80
Ramipril	10
Trandolapril	4
Sacubitril/Valsartan*	194/206*
ARB	
Candesartan	32
Losartan	150
Valsartan	320
Beta-blocker	
Bisoprolol	10
Carvedilol	50
Metoprololsuccinat, Metoprolol	200
Nebivolol	10
MRA	
Eplerenone	50
Spironolactone	50

* Considered as (exactly) one treatment with combined total daily target dose of 400 mg.

The following drugs do not have an indication for HF and will yield the patient being classified as non-adherent: Moexipril (ACEi), Zofenopril (ACEi), Eprosartan (ARB), Irbesartan (ARB), Olmesartan medoxomil (ARB), Telmisartan (ARB), Atenolol (Beta-blocker), Betaxolol (Beta-blocker), and Sotalol (Beta-Blocker).

The HF indication and the daily target dose of any ACEi, beta-blocker, ARB or MRA neither included in this list nor in [Table 4-3](#) but occurring in the data (according to the above described implementations) will be identified separately and confirmed by Novartis.

In case the dose is not given in “total daily dose in mg”, it will be converted respectively.

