2.1 Primary objective(s)

To assess if NT-proBNP measurement-guided cardiologist-referral of CHF patients, who are currently judged by their primary care physician as being clinically stable*, leads to optimization of HF treatment, defined as adherence[#] to level I-A treatment recommendations of the current[§] ESC guidelines for the treatment of HF.

***Note:** Within this study, clinically stable patients are defined as those patients, who by the judgement of their primary care physician currently do not require and, in the last 3 months prior to the baseline visit have not had, any change in their pharmacological or device treatment of HF.

[figure not shown]
#Note: Adherence to the recommendations of the ESC guidelines within this study is defined as the prescription of all HF specific drugs with level I-A recommendation for a given patient's clinical status at a dose $> 50\%$ of the recommended daily dose.

§Note: Current ESC guidelines are those which are in force on the date the patient signs the informed consent form.

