9.8 Sample size calculation

The study is powered to estimate the proportion of patients switching from a non-ESC guideline recommendations-adherent treatment to regimen adhering to these recommendations after referral to a cardiologist based on all patients who at baseline are judged by their primary care physician to be clinically stable and show NT-proBNP levels ≥ 600 pg/ml.

Based on the data from Dahlstrom et al ([Dahlstrom, Hakansson et al. 2009](#)), showing that only 20% of patients followed by primary care physician receive both Renin-Angiotensin System inhibitors and beta-blockers at a dose $\geq 50\%$ of the recommended, we conservatively assume 20% as the percentage of CHF patients that will be treated in accordance to the ESC guidelines (i.e. prescription of any drugs with level I-A recommendation for a given patient's

clinical status at a dose of > 50% of the recommended daily dose) at baseline (Visit 1). In addition, we assume that after referral to a specialist (Visit 2), the proportion will increase to 30% ([Maggioni, Anker et al. 2013](#)). Although there are no data in the literature measuring the clinical impact of increasing guideline-adherence of treatment in HF, it has been clearly demonstrated that a 10% increase in acute coronary syndrome is clinically highly significant. In fact, for every 10% increase in guideline-adherence at a hospital center, the in-patient's mortality odds ratio falls by a corresponding 39%. Similarly, for every 10% increase in appropriate dosing, the patient's mortality odds ratio falls by a corresponding 18% ([Mehta, Chen et al. 2015](#)).

We further assume that around 25% of patients without ESC guideline recommendations-adherent treatment at baseline (i.e. prior to referral to a cardiologist) will receive optimization (i.e. ESC guideline adherent treatment) of their HF treatment post referral to the cardiologist. This proportion can be estimated with a precision of $\pm 2\%$ using a 95%-CI by including 1,728 patients into the analysis; for subgroup analyses (e.g. on country level) the range of a 95%-CI increases, however it is still possible to estimate the proportion with a precision of $\pm 5\%$ for subgroups of 300 patients.

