7.4.2 Adherence to ESC guidelines (primary analysis)

For each patient, HF treatment at every visit will be classified with respect to adherence to ESC guidelines on level 1 and level 2 as outlined in [Section 4.5.1](#). Respective frequency distributions of adherence (yes, no) will be provided for the Follow-up Set for every visit.

The primary analysis will be performed on guideline adherence level 1 (as described in [Section 4.5.1](#)) as follows: based on the patients in the Follow-up Set treated not according to ESC guidelines at Visit 1, absolute and relative frequencies of A2 will be provided. The proportions within this analysis will be calculated twice, with and without considering missing values for A2. 95%-CIs will be provided for the proportions.

This analysis of A2 will be repeated for all patients in the Follow-up Set treated according to guidelines (level 1) at Visit 1.

For sensitivity, the analyses of A2 conditional to guideline adherence at Visit 1 will be repeated for guideline adherence level 2 (drug type and dose).

For the Enrolled Set, adherence to ESC guidelines (level 1 and level 2) will be analysed at Visit 1, additionally stratified by inclusion into the prospective period of the study.

In addition, the analyses of guideline adherence with respect to drug type will be repeated without taking into account the indication of the applied medications. This means, patients taking an ACEi, ARB, Beta-Blocker or MRA without HF indication will not automatically be classified as non-adherent in this analysis. Instead, these drugs will be included in the analysis and can contribute to a guideline adherent treatment of the patient.

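### Guideline adherence needs doses above 50% of target in the protocol and SAP objective but at or above 50% in SAP Table 4-2; the undeclared change affects the level 2 analyses, not the SAP's primary analysis

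*SAP*

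**What the plan says.** **The objective.** The notes to the primary objective in the protocol summary, Protocol 2.1 and SAP 3.1 define adherence as prescription of all level I-A heart failure drugs "at a dose > 50% of the recommended daily dose". Protocol 9.8 repeats the strict inequality when it restates the study definition: "clinical status at a dose of > 50% of the recommended daily dose".

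**The operative rule.** SAP 4.5.1 sets up two levels, drug type (level 1) and drug type plus dose (level 2), and says of Table 4-2: "The exact definitions of both levels of guideline adherence are provided in" that table. The level 2 row requires "dosage of all respective guideline drugs ≥ 50% of the recommended target dose".

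**Where each level is used.** SAP 7.4.2 states: "The primary analysis will be performed on guideline adherence level 1". Level 2 is used for three things: the sensitivity repeat of A2 conditional on Visit 1 adherence, the by-visit frequencies in the Follow-up Set, and the Visit 1 description in the Enrolled Set. The subgroup analyses of A2 in SAP 7.11 are on level 1.

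**Declared deviations.** SAP 2.5 says: "The SAP is consistent with the underlying protocol". It adds that substantial departures are described and that the SAP's methods bind the programmers. SAP 7.13 lists three departures: heart failure medication analysed by visit, the cross-table split into separate tables, and country stratification limited to specified analyses. The dose threshold is not among them.

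**The concern.** The SAP states one threshold in its objective and another in the table from which the variable will be derived. Nothing tells the reader that the rule changed. A study report that follows the SAP would print the objective with a strict inequality beside level 2 results computed with a non-strict one.

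This matters because the protocol's definition of adherence includes dose, and level 2 is the only place where the SAP keeps that element. A reader who wants the result closest to the protocol's definition will turn to level 2. For the conditional analysis, the operator decides both who is non-adherent at Visit 1 (the denominator) and who counts as switched at Visit 2 (the numerator).

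**Working it through.** **Step 1. The statements side by side.**

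| Place | Threshold |
|---|---|
| Protocol summary, primary objective note | > 50% |
| Protocol 2.1 | > 50% |
| Protocol 9.8, study definition | > 50% |
| Protocol 9.8, source of the 20% baseline figure | ≥ 50% |
| SAP 3.1 | > 50% |
| SAP 4.5.1, Table 4-2, level 2 | ≥ 50% |

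Protocol 9.8 prints both operators, so the difference is not a text-extraction artefact.

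**Step 2. Who is classified differently.** The rules differ only at exactly 50%, and all required drugs must pass together. A patient changes class only if (a) the drug-type criterion is met, (b) no required drug is below 50% of target, and (c) at least one is at exactly 50%.

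An illustrative grid shows how far these conditions narrow the group. Let each required class be absent or at 25, 50, 75 or 100% of target.

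- LVEF ≤ 35%, three classes: 5³ − 4³ = 125 − 64 = 61 regimens contain a drug at exactly 50%. Of these, 3³ − 2³ = 27 − 8 = 19 change class, and 61 − 19 = 42 are non-adherent under both rules.
- LVEF > 35%, two classes: 5² − 4² = 25 − 16 = 9 regimens. Of these, 3² − 2² = 9 − 4 = 5 change class and 4 do not.

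These are counts of possible regimens, not of patients.

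**Step 3. Effect on the level 2 switch proportion.** Classify each patient at Visits 1 and 2 as b (drug type not met, or a required drug below 50%), e (condition of Step 2 met) or a (all required drugs above 50%). Let n_b and n_e be the Visit 1 totals, and let n_ba, n_be and n_ea count the moves between states.

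- Under ≥ 50%: p₁ = (n_be + n_ba) / n_b
- Under > 50%: p₂ = (n_ba + n_ea) / (n_b + n_e)

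Rearranging, p₂ > p₁ exactly when n_ea > n_be + p₁ × n_e. The documents give none of these counts, so neither the direction nor the size of the difference is known in advance.

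**Step 4. Is exactly half target plausible?** Halving targets in SAP Table 4-3 gives, for example, ramipril 10/2 = 5, bisoprolol 10/2 = 5, carvedilol 50/2 = 25, spironolactone 50/2 = 25 and sacubitril/valsartan 400/2 = 200 mg per day. Protocol 1.1 cites a cardiology registry with on-target dosing in 29, 24 and 17% of cases for the three drug classes, so doses below target were common there. Neither fact gives the share at exactly half.

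As an assumption only, let a share q of patients at or above half target sit exactly at half for each drug, independently. The share of patients adherent under ≥ 50% who stay adherent under > 50% is then (1 − q)^k:

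- q = 0.2: 0.8³ = 0.512 for three drugs, 0.8² = 0.64 for two.
- q = 0.5: 0.5³ = 0.125 for three drugs, 0.5² = 0.25 for two.

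This concerns the adherent group, not the switch proportion, and both q and independence are assumed.

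**Step 5. The 20% in Protocol 9.8.** The plan's figures reproduce with 20% adherent at baseline: 2,160 × (1 − 0.20) = 1,728. That 20% comes from a study that counted patients "at a dose $\geq 50\%$ of the recommended" dose, yet it is applied to the stricter definition. With all else in that source held fixed, the strict rule cannot give more than 20% adherent. The non-adherent share of 2,160 would then be at least 1,728, so this mismatch does not make the planned number too small.

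**The case against.** The strongest reply is about scope. The SAP's primary analysis and its A2 subgroup analyses are on level 1, which has no dose criterion, so the operator enters neither. That stands. A reader might infer that the primary result changes with the threshold; the SAP as written does not support this. It would follow only if the separate question of level 1 against level 2 were settled by bringing dose back into the primary analysis, and that question should be judged on its own.

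A reader might also infer that every patient on half the target dose is classified in opposite ways. Step 2 shows otherwise: a patient who lacks a required class, or has another required drug below 50%, is non-adherent under both rules.

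It is also fair to say that the programmed rule is not in doubt. Table 4-2 is named as the exact definition and the SAP's methods are mandatory for programming, so ≥ 50% will be run. The defect is therefore an undeclared departure from the stated definition, not an undetermined analysis.

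Finally, the illustrative percentages in Step 4 are not evidence of size. That stands too. None of these replies removes the contradiction between SAP 3.1 and Table 4-2, or its absence from SAP 7.13.

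**Conclusion.** The contradiction is confirmed, both within the SAP and between SAP and protocol, and it is undeclared. It affects the level 2 sensitivity analysis of A2 conditional on A1, the level 2 by-visit frequencies and the level 2 Visit 1 description in the Enrolled Set. It also carries into repeats of these under the missing-LVEF substitution (SAP 7.10) and for Belgian centres (SAP 7.11 and 7.12). SAP 7.6 stratifies NT-proBNP by adherence without naming the level; the operator would matter there only if level 2 is meant.

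The patients concerned are those who meet the drug-type criterion and whose lowest-dosed required drug is at exactly 50% of target. Their number cannot be derived from the documents, and the direction of the effect on the switch proportion is open. The point should be fixed before analysis, but it does not threaten the primary analysis as the SAP defines it. This conclusion does not depend on which threshold is chosen, and none is recommended here.

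**What to change.** 1. Reconcile the protocol summary, Protocol 2.1 and 9.8, SAP 3.1 and SAP Table 4-2 so that one operator is used throughout.
2. List the choice in SAP 7.13, and qualify the consistency statement in SAP 2.5 accordingly.
3. Note for Protocol 9.8 which operator the 20% baseline figure refers to. SAP 4.2 says recruitment and data collection stopped in March 2018, so if the protocol is no longer amended, this note can sit in SAP 7.13.
4. Report the level 2 results (A1, A2, and A2 conditional on A1) under the other operator as well, with the number of patients who change class at each visit. Items 1 and 2 remove the contradiction; this item replaces an unknown size with a count.

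The cost is a wording change in the SAP and one further run of an existing program with a single comparison altered. No new data are needed.
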